1.2. Study endpoints

The endpoints for the primary objective are:

- The incidence of DLT(s) starting from the lead-in dose (LID) period to the end of each cycle of treatment of S64315 in combination with azacitidine.
- The incidence and severity of adverse events (AEs) and serious adverse events (SAEs) according to the National Cancer Institute Common Terminology Criteria for Adverse Events (NCI-CTCAE) version 5.0.
- The recording of any change or addition of a new concomitant treatment.
- The laboratory tests: haematology with differential, blood biochemistry, thyroid function, blood coagulation, urinary analysis, hepatitis markers, Tumour Lysis Syndrome (TLS) monitoring, cardiac markers follow up.
- The complete physical examination, Eastern Cooperative Oncology Group (ECOG) performance status and vital signs measurements.
- The electrocardiogram (ECG) parameters and cardiac function assessment.
- The left ventricular ejection fraction (LVEF).
- The dose interruptions, reductions and dose intensity.

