1.3.1. Dose administration schedule and escalation

The initial schedule (see [Figure \(1.3.2\) 1](#)) will consist of a lead-in period followed by 28-day cycles when S64315 will be administered in combination with azacitidine. S64315 will be administered via intravenous (IV) infusion over at least 2 hours once every week, azacitidine will be administered via subcutaneous (SC) injection once daily for 7 consecutive days.

The schedule will be as follows:

- A 2-week LID period with S64315 fixed LID1 of 25 mg on day -13 (D-13) and S64315 fixed LID2 of 50 mg on D-6, followed by

- 28-day cycles (Cx) of combination treatment period with S64315 administered on CxD2, CxD9, CxD16 and CxD23, and 75 mg/m² of azacitidine administered daily for 7 days from CxD1 to CxD7 followed by a rest period of 21 days.

On days of concomitant administration of S64315 and azacitidine (CxD2), azacitidine should be administered 2 hours (± 10 min) prior to S64315. The starting dose of S64315 after the lead-in period will be 50 mg. A panel of doses (see [Table \(1.3\) 1](#) from 25 mg (-1) and up to 250 mg could be explored according to the dose escalation process of the Bayesian Logistic Regression Model (BLRM).

During the dose escalation phase, at each new dose level, the IMPs will be firstly administered to one patient. If no medically important or life-threatening toxicity occurs during a 1 week observation period, the subsequent patients will be allowed to start treatment without further delays between subsequent patients. The dose increase between two dose levels will be guided by the observed toxicities.

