 - Number of cycles delayed (1, 2, > 2) during treatment period (including LID).
- Specifically for S64315, the summary of treatment compliance will also will include:
 - Dose modified (Yes/No) during treatment period (including LID).
 - Number of dose modifications during treatment period (including LID).
 - Number of dose modifications (1, 2, > 2) during treatment period (including LID).
 - Time to first dose modification (days) during treatment period (including LID).
 - Partial dose administered (Yes/No) during treatment period (including LID).

- Number of cycles with partial dose for S64315 during treatment period (including LID).
- Number of cycles with partial dose for S64315 (1, 2, > 2) during treatment period (including LID).
- Specifically for azacitidine, the summary of extent of exposure will include:
 - Average number of days dosed per cycle with planned dose level for azacitidine overall.
 - Average number of days dosed overall.
 - Number of azacitidine interruption days.

* Applicable for both S64315 and azacitidine if not specified.

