A dose modification is defined according to the S64315 infusion e-CRF page (Has the dose been modified since the last infusion (Yes/No), with a dose level different from the dose level at previous infusion).

Number of dose modifications for S64315 experienced by a patient over the treatment period will be calculated among patients experiencing a dose modification.

Time to first dose modification for S64315 will be calculated among patients experiencing a dose modification from the first study drug intake until the first dose modification.

Partial dose administered for S64315

A partial dose administered is defined according to the S64315 infusion e-CRF page (Was full dose administered ? (Yes/No))

Number of cycles with partial dose experienced by a patient over the treatment period will be calculated among patients.

Number of days dosed for azacitidine

The number of days dosed for azacitidine is defined as the total number of days with azacitidine intake (overall and by cycle).

Average number of days dosed per cycle for azacitidine

The average number of days dosed per cycle for azacitidine is defined as the total number of days dosed for azacitidine divided by the number of cycles according to the period of interest (i.e. for overall period: number total of cycles / for each cycle: 1):

$$\text{Average days dosed per cycle} = \frac{\text{Total number of days dosed}}{\text{Number of cycles}}$$

Number of days dosed with planned dose level for azacitidine

The number of days dosed with planned dose level for azacitidine is defined as the total number of days with azacitidine intake corresponding to the planned dose level of 75 mg/m² (the actual dose administered is equal to 75mg/m² or within the interval 75 ±7.5 mg/m²).

Average number of days dosed per cycle with planned dose level for azacitidine

The average number of days dosed with planned dose level for azacitidine per cycle is defined as the total number of days dosed with planned dose level for azacitidine divided by the number of cycles according to the period of interest (i.e. for overall period: number total of cycles / for each cycle: 1):

$$\text{Average days dosed with planned dose level per cycle} = \frac{\text{Total number of days dosed with planned dose level}}{\text{Number of cycles}}$$

Real administrated dose of azacitidine will be recorded directly from azacitidine injection e-CRF page (Administered dose (mg)).

Planned dose intensity (PDI) for azacitidine:

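### The S64315 dose-modification outputs do not exclude the scheduled lead-in steps, and the SAP defines no dedicated dose-reduction summary for either drug

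*SAP*

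**What the plan says.** SAP 4.2.1.5 sets two conditions for an S64315 dose modification, both taken from the infusion page: "Has the dose been modified since the last infusion (Yes/No), with a dose level different from the dose level at previous infusion". The second condition, "with a dose level different from the dose level at previous infusion", gives no direction of change and does not mention the scheduled steps.

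SAP 3.2.5.1 builds four rows on this definition, all covering the lead-in: "Dose modified (Yes/No) during treatment period (including LID"), the number of modifications, that number in classes (1, 2, more than 2), and "Time to first dose modification (days) during treatment period (including LID"). SAP 4.2.1.5 runs the clock for the last of these "from the first study drug intake until the first dose modification", which for a treated patient is LID1.

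SAP 1.3.1 fixes the lead-in for everyone: "S64315 fixed LID1 of 25 mg on day -13 (D-13) and S64315 fixed LID2 of 50 mg on D-6". The provisional full doses in SAP Table (1.3) 1 are 25, 50, 100, 200 and 250 mg.

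SAP 1.2 lists among the endpoints of the primary objective: "The dose interruptions, reductions and dose intensity". Protocol Table (3.4) 1 names the same endpoint.

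For azacitidine, SAP 3.2.5.1 and 4.2.1.5 cover interruptions, cycle delays, days dosed, days at the planned level, dose intensity (DI) and relative dose intensity (RDI). They have no modification or reduction output, although Protocol Table (8.12) 2 foresees azacitidine cycles at 50% or 33% of the dose.

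**The concern.** The level-difference condition is met by design at LID2 in every cohort, and again at C1D2 in every cohort except 50 mg. Whether those steps enter the table then depends only on how each site reads one Yes/No item, and the SAP does not say how a scheduled step should be treated. Protocol 4.1.1 keeps the lead-in doses fixed throughout the study, so no discretionary level change is foreseen between LID1 and LID2. Including the lead-in can therefore add little except scheduled steps.

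The second gap is the endpoint itself. Interruptions and dose intensity are derived, but reductions are not. In a dose-finding study that stopped after escalation, the number of patients at each dose level who needed a reduction, and when, is one of the main tolerability results. As written, the nearest S64315 output is an undirected count that may mix reductions with scheduled steps. Azacitidine has no corresponding count.

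**Working it through.** The documents give no figure for this point, so there is nothing to reproduce. The check applies the SAP rule to the planned schedule.

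**Inputs**
- Lead-in 25 mg on D-13 and 50 mg on D-6; full dose from C1D2 (SAP 1.3.1).
- Full dose 25, 50, 100, 200 or 250 mg (SAP Table (1.3) 1), with no reduction below 25 mg.
- Duration = later date − earlier date + 1 day, unless otherwise specified (SAP 4.1.4).
- LID2 may be postponed by 1 to 5 days for an adverse event (Protocol 5.8.1).
- Assumption: sites answer Yes at a scheduled change of level. If they answer No, the scheduled-step counts below become 0.

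**Counts.** The number of infusions whose level differs from the previous one, for a patient fully on schedule, and for a patient with a single one-level reduction at cycle 2:

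| Cohort | Planned sequence (mg) | Compliant, with lead-in | One reduction, with lead-in | Compliant, from C1D2 | One reduction, from C1D2 |
|---|---|---|---|---|---|
| 25 mg | 25, 50, 25 | 2 | not applicable | 0 | not applicable |
| 50 mg | 25, 50, 50 | 1 | 2 | 0 | 1 |
| 100 mg | 25, 50, 100 | 2 | 3 | 0 | 1 |
| 200 mg | 25, 50, 200 | 2 | 3 | 0 | 1 |
| 250 mg | 25, 50, 250 | 2 | 3 | 0 | 1 |

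With the lead-in included, a patient at 50 mg with a true reduction (2) cannot be told apart from a compliant patient at 100 mg (2). The compliant counts also differ between cohorts for a reason unrelated to tolerability.

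**Time to first modification**, if LID2 counts:
- On schedule: (−6) − (−13) + 1 = 8 days.
- LID2 postponed by the maximum 5 days: 7 + 5 + 1 = 13 days.

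**Additional lead-in.** Protocol 6.1.2 requires a new lead-in after an S64315 interruption of 28 days or more, except in CR/CRi. Assuming the same 25 and 50 mg, a patient at 100 mg who restarts follows 100, 25, 50, 100. That is 3 further scheduled changes, the first of them downward.

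**Can RDI stand in for reductions?** Take one 4-week cycle in the 100 mg cohort, with planned intensity 100 mg/week:
- Reduced to 50 mg for all four infusions: 4 × 50 = 200 mg; 200/4 = 50 mg/week; RDI 50%.
- Two of four infusions omitted at full dose: 2 × 100 = 200 mg; RDI 50%.

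Both fall in the SAP class from 35% to below 65%, so RDI does not identify a reduction.

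**The case against.** A reader might infer three stronger things, and the documents support none of them.

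1. *That every patient will be shown as modified.* The SAP requires a Yes on the e-CRF item as well as a different level. Protocol 8.12 uses the term dose modification for adaptations to toxicity, so a site following that usage would answer No at a scheduled step. The e-CRF completion instructions are not in the documents, and the table shells are in a separate document (SAP 1). The counts above are what the rule permits, not a forecast.

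2. *That time to first modification is 8 days for everyone, whatever the toxicity.* LID2 can be postponed for an adverse event. A patient stopped before LID2 has no scheduled step at all.

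3. *That reductions are never reported.* SAP 3.4.2 describes treatment-emergent adverse events by action taken on the study drugs. Its categories are not listed, so dose reduction may be among them. Not resuming S64315 at the same dose because of related toxicity is itself a DLT criterion (SAP Table (4.2.3.1) 1), so some cycle 1 reductions would appear in the DLT table. RDI reflects reductions in both drugs. A full azacitidine cycle at 50% or 33% gives zero days at the planned level.

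The missing direction also has limited weight after C1D2. SAP 1.3.1 says no intra-patient escalation will be conducted, and Protocol 8.12 allows re-escalation only with documented Sponsor agreement. Most later changes are therefore reductions. These rows are descriptive, sit in an abbreviated report, and do not feed the BLRM, the DLT rate or the MTD.

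What remains is that the SAP does not settle whether scheduled steps count, and none of the indirect sources is specified to give patients with a reduction, number of reductions or time to first reduction by dose level. Action taken is tied to adverse events, the DLT table in SAP 3.4.1 stops at the end of cycle 1, and RDI mixes omitted, delayed, partial and reduced doses.

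**Conclusion.** The point holds in two parts. First, the S64315 modification rows can mix scheduled lead-in steps with real changes. Conditional on Yes at scheduled steps, that adds 1 modification per compliant patient at 50 mg and 2 at every other provisional level, and places the first modification at 8 to 13 days. The size actually reached depends on e-CRF practice that the documents do not show. Second, and without any such condition, a listed endpoint of the primary objective has no dedicated summary in the SAP for either drug. The indirect outputs soften this but do not replace it. The effect is confined to the exposure and tolerability tables; dose-escalation decisions are untouched. It is worth correcting because the remedy is cheap.

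**What to change.** In SAP 4.2.1.5 and 3.2.5.1:

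- State that the scheduled steps of the initial lead-in (LID1 to LID2 to C1D2), and those of any additional lead-in period including the return to full dose, are not dose modifications.
- From C1D2, derive an S64315 reduction as a prescribed level below the last prescribed full-dose level, ignoring lead-in infusions, with the assigned dose as the reference at C1D2. Comparing only with the immediately preceding infusion would not do, because the first infusion of an additional lead-in could then count as a reduction.
- Count increases separately from reductions.
- Base both on recorded doses rather than on the Yes/No item alone. Protocol 6.2 already requires prescribed doses and dose changes for both drugs to be entered in the eCRF.
- Report, by dose level and overall, patients with at least one reduction, number of reductions, and time from C1D2 to first reduction.
- For azacitidine, add a patient-level reduction count from recorded doses against 75 mg/m². The ±7.5 mg/m² band that SAP 4.2.1.5 already uses for the planned level can serve as the tolerance.

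The cost is SAP wording and programming. No new data are needed.

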3.2.5. Treatments of patients

3.2.5.1. Extent of treatment exposure and treatment compliance

Details concerning definition on extent of exposure, treatment compliance are provided in [Appendix 4.2.1.5](#).

For S64315 and azacitidine separately the frequency distribution (n, %) or descriptive summary statistics (n, mean, SD, median, min, max, median, Q1, Q3) as applicable will be provided in

patients of the SS by planned dose level combination and overall for variables measured on a nominal scale according to the following classes:

- Extent of exposure*:
 - The global treatment duration (combined measure for S64315/azacitidine): summary statistics.
 - Treatment duration (weeks) overall and by treatment period (LID/Combination treatment).
 - Treatment duration (weeks) during combination treatment period (i.e., excluding LID) (< 4 weeks, [4-12[weeks, [12-24[weeks, [24-36[weeks, [36-48] weeks, >48 weeks).
 - LID duration ([0-1] week, [1-2] weeks and > 2 weeks).
 - Number of cycles (1 cycle, 2 cycles, 3-6 cycles, 7-10 cycles, > 10 cycles) during the combined treatment period.
 - Number of patients by cycle (LID, Cycle 1, Cycle 2, etc).
- Treatment compliance*:
 - Cumulative dose (mg) for S64315/ Cumulative dose (mg/m²) for azacitidine overall, by cycle (including LID), and for combination treatment.
 - Dose intensity (DI) (mg/week) for S64315/ DI (mg/m²/day) for azacitidine overall, by cycle (including LID), and for combination treatment.
 - Relative Dose Intensity (RDI) (%) for S64315/azacitidine overall, by cycle (including LID), and for combination treatment.
 - RDI for S64315(< 35%, [35-65[%, [65-100[%, ≥ 100%) overall, by cycle, and per treatment period (LID/Combination treatment).
 - RDI for azacitidine (< 62%, [62-85[%, [85-100[%, ≥ 100%) overall, by cycle, and per treatment period (Combination treatment).
 - Treatment interruption (Yes/No) during treatment period (including LID).
 - Reason of treatment interruption (Medical reason, Non-medical reason, Missing).
 - LIDLIDNumber of cycles with at least one treatment interruption for S64315 during treatment period (including LID).
 - Number of cycles with at least one treatment interruption for azacitidine during treatment period.
 - Cycle delayed (Yes/No) during treatment period (including LID).
 - Reason for cycle delayed (Medical reason, Non-medical reason, Missing).
 - Number of cycles delayed during treatment period (including LID).

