4.1.2. First and last IMP intakes dates

For patients having taken at least one dose of IMP (S64315 or azacitidine), the dates of first and last IMP (S64315 or azacitidine) intake on the analysis period (including LID) will be defined as follows:

- The date of the first IMP intake within the analysis period (including LID).
- The date of the last IMP intake within the analysis period (including LID):
max(last intake date of last cycle of S64315, last intake date of last cycle of azacitidine).

Note: For azacitidine, cycles with both missing first and last IMP intake dates and with administered dose missing or equal to 0 will not be taken into account.

After selection of the dates of first and last IMP intake as defined above, if these dates are missing or incomplete, the following substitution rules will be applied:

Table (4.1.2) 1 - Substitution rules of IMP intake dates

Date to substitute	Substituted date
First IMP (S64315 or azacitidine) intake	
./mmm/yyyy
 
Inclusion date if complete with same month and year Otherwise: 01/mmm/yyyy
 
./.../yyyy
 
Inclusion date if complete with same year Otherwise: 01/JAN/yyyy
 
./.../....
 
Inclusion date if complete

Last IMP (S64315 or azacitidine) intake	
./mmm/yyyy
 
Last available date* if same month and year Otherwise: Last day of the month/mmm/yyyy
 
./.../yyyy
 
Last available date* if same year Otherwise: 31/DEC/yyyy
 
./.../....
 
Last available date* Last available date**

Notes:

- Missing dates will be substituted only for patients having taken at least one dose of study treatment:
./mmm/yyyy = missing day.
./.../yyyy = missing day and month.
./.../.... = totally missing date.
***** Last available date (only for patients included) is defined as date of death if patient died, and as maximum date among completed dates relative to patient's information otherwise.

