Note: The duration of the last cycle for S64315 will be estimated to be 4 weeks for the calculation of dose intensity and relative dose intensity at the last cycle.

Cycle duration for azacitidine

Duration of cycle i (weeks) for azacitidine is defined as [first IMP intake of cycle $(i+1)$ – first IMP intake of cycle i] / 7.

Of note,

- The duration of the last cycle for azacitidine will be defined as [(last intake of last cycle + 21 days) – first intake of last cycle + 1] / 7.

Numbers of cycles for S64315/azacitidine

The number of cycles with study drug intake for S64315/azacitidine will be defined based on patient exposure data while on treatment excluding S64315 LID period. A patient is considered to enter in a cycle if there is at least one intake date.

Real administrated dose of S64315 will be recorded directly from S64315 infusion e-CRF page. For information, the administrated dose is recorded in mL within e-CRF. The conversion of the real administrated dose in mg is directly calculated by the data manager. Little variation between planned dose and real administrated dose can be expected due to feasibility (IMP preparation and injection).

Planned dose intensity (PDI) for S64315 (mg/week)

Planned dose intensity (PDI) for S64315 (mg/week)	Schedule (QW)
	4 intakes per cycle / 1 intake per LID week
Dose Level -1: 25 mg*	25 mg/ week*
Dose Level 1: 50 mg**	50 mg/ week**
Dose Level 2: 100 mg	100 mg/ week
Dose Level 3: 200 mg	200 mg/ week
Dose Level 4: 250 mg	250 mg/ week

* LID1 dose.

** LID2 dose

However, it is possible that intermediate or higher dose levels are added during the course of the study.

Cumulative dose for S64315

The cumulative dose (mg) for S64315 per patient in a time period (during the treatment period including LID or per cycle) is the sum of the total dose levels that the patient received within that period according to the compliance.

$$\text{Cumulative dose (mg)} = \sum_{\text{timeperiod}} (\text{Real Administrated dose (mg)}).$$

Dose intensity (DI) for S64315

The dose intensity (mg/ week) for S64315 per patient is defined as the cumulative dose (mg) received during the treatment period divided by the total treatment duration in weeks, including LID period.

$$DI \left(\frac{\text{mg}}{\text{wk}} \right) \text{ per patient} = \frac{\text{Cumulative dose (mg)}}{\text{Treatment duration (weeks)}}$$

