Planned dose intensity (day): 75 mg/m²/day (fixed).

Planned dose intensity (cycle or overall): (75 mg/m²/day (fixed) * 7) / 28.

Cumulative dose for azacitidine

The cumulative dose (mg/m²) for azacitidine per patient during a time period (during the treatment period or per cycle) is the sum of the total dose levels that the patient received between the first and last treatment intake according to the compliance.

$$\text{Cumulative dose (mg/m}^2\text{)} = \sum_{\text{timeperiod}} \left(\frac{\text{Real Administrated dose (mg)}}{\text{BSA (m}^2\text{)}} \right).$$

Dose intensity (DI) for azacitidine

The dose intensity (mg/m²/day) for azacitidine per patient is defined as the cumulative dose (mg/m²) received during the treatment period divided by the overall treatment duration of azacitidine.

$$DI \left(\frac{\text{mg/m}^2}{\text{day}} \right) \text{ per patient} = \frac{\text{Cumulative dose (mg/m}^2\text{)}}{\text{Overall treatment duration of azacitidine}}.$$

The dose intensity (mg/day) for azacitidine per cycle is defined as the cumulative dose (mg) received during the cycle divided by the cycle duration of azacitidine.

$$DI \left(\frac{\text{mg/m}^2}{\text{day}} \right) \text{ at cycle } i = \frac{\text{Cumulative dose (mg/m}^2\text{) received at cycle } i}{\text{Cycle } i \text{ duration of azacitidine}}.$$

Relative dose intensity (RDI) for azacitidine

The relative dose intensity (%) for azacitidine per patient measures the percentage of the total trial dose planned that was really administered. It is defined as the ratio of the dose intensity (mg/m²/day) to the initial planned dose intensity (mg/m²/day).

$$RDI (\%) \text{ per patient} = \frac{DI (\text{mg/m}^2/\text{day})}{\text{Planned dose intensity (mg/m}^2/\text{day)}} * 100.$$

The relative dose intensity (%) for azacitidine per cycle is defined as the ratio of the dose intensity (mg/m²/day) at cycle *i* to the planned dose intensity (mg/m²/day).

$$RDI (\%) \text{ at cycle } i = \frac{DI \text{ at cycle } i (\text{mg/m}^2/\text{day})}{\text{Planned dose intensity at cycle } i (\text{mg/m}^2/\text{day)}} * 100.$$

Treatment interruption for azacitidine

A treatment interruption is defined according to the azacitidine injection e-CRF page (Did the patient receive at least one azacitidine injection (Yes/No)).

Number of cycles with at least one treatment interruption for azacitidine experienced by a patient over the treatment period will be calculated.

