Number of azacitidine interruption days experienced by a patient over the treatment period will be calculated among patients experiencing a treatment interruption.

The number of azacitidine interruption days is the number of days on which azacitidine was scheduled to be administered but was not actually administered.

Cycle delay for azacitidine

A cycle delay is defined according to the azacitidine injection e-CRF page (Was the injection day postponed (Yes/No) at D1 of the cycle). Moreover, a cycle delay of cycle *i* will be also considered if the duration of the cycle *i-1* is higher than (*). In case of missing cycle delay

reason, reason of cycle delay will be considered as unknown. The delay in days will be derived, based on the dates of administration.

For $i > 1$, Delay (days) of cycle $i = (\text{first IMP intake of cycle } i) - (\text{first IMP intake of cycle } i-1 + x \text{ days})$

(*): 30 days for regular cycle (theoretical cycle duration + 2 days for potential technical or logistical difficulty). In the delay duration formulae above $x=30$.

Number of cycles delayed for azacitidine experienced by a patient over the treatment period will be calculated among patients experiencing a cycle delay.

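### If its e-CRF item is answered once per cycle, the SAP's azacitidine interruption flag catches only cycles with none of the 7 injections; cycles with 1 to 6 count as uninterrupted

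*SAP*

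**What the plan says.** SAP 4.2.1.5, under the azacitidine interruption heading, gives a single definition: "A treatment interruption is defined according to the azacitidine injection e-CRF page (Did the patient receive at least one azacitidine injection (Yes/No". This feeds the azacitidine interruption Yes/No and two further lines in SAP 3.2.5.1: "Reason of treatment interruption (Medical reason, Non-medical reason, Missing" and "Number of cycles with at least one treatment interruption for azacitidine during treatment period".

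The same part of 4.2.1.5 then defines a day-level quantity: "The number of azacitidine interruption days is the number of days on which azacitidine was scheduled to be administered but was not actually administered". It limits who contributes to it: "Number of azacitidine interruption days experienced by a patient over the treatment period will be calculated among patients experiencing a treatment interruption".

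Two other rules deal with cycles in which nothing was given. SAP 4.2.1.5 says, on the number of cycles: "A patient is considered to enter in a cycle if there is at least one intake date". SAP 4.1.2, when setting first and last intake dates, disregards azacitidine "cycles with both missing first and last IMP intake dates and with administered dose missing or equal to 0".

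SAP 1.2 lists dose interruptions among the endpoints for the primary (safety) objective.

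**The concern.** The item asks whether any injection was received. Asked once for a 7-injection cycle, it is answered No only when all seven were missed, so the flag would record whole cycles omitted rather than interruptions of dosing. The day count uses a different and stricter idea, any scheduled day missed, but only patients with an interruption enter it, and no other definition of such a patient is given. Patients whose cycles were all partly dosed would have missed days and still be left out of the line meant to report them.

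The one kind of cycle that is flagged also fits poorly with the cycle-entry rule, which requires an intake date. If that rule is applied per drug, the flagged cycle is not one the patient entered.

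Four outputs are at stake: the azacitidine interruption Yes/No, its reasons, the count of interrupted cycles and the interruption-days line. Since the SAP fixes neither the item's frequency nor the answer that counts, two programmers could produce different tables from the same data.

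**Working it through.** **Inputs.** Seven scheduled injections per 28-day cycle (SAP 1.3.1). Planned dose intensity per cycle or overall is 75 × 7 / 28 = 18.75 mg/m²/day (SAP 4.2.1.5). The last azacitidine cycle runs from its first intake to its last intake plus 21 days, inclusive (SAP 4.2.1.5). RDI classes are cut at 62%, 85% and 100% (SAP 3.2.5.1). The plan states no figure for this point, so there is none to reproduce.

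**Assumptions.** Full dose at each injection, consecutive injections from D1, 28-day spacing, durations in days, and the e-CRF item answered once per cycle with No meaning interruption.

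**One cycle with k injections.** In a non-last cycle, RDI = (75k/28)/18.75 = k/7. In the last cycle the duration is k + 21 days, so RDI = [75k/(k + 21)]/18.75 = 4k/(k + 21).

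| k | Flagged, per-cycle item | Missed days (7 − k) | RDI, non-last cycle | RDI, last cycle |
|---|---|---|---|---|
| 7 | No | 0 | 100% | 100% |
| 6 | No | 1 | 85.7% | 88.9% |
| 5 | No | 2 | 71.4% | 76.9% |
| 4 | No | 3 | 57.1% | 64.0% |
| 3 | No | 4 | 42.9% | 50.0% |
| 2 | No | 5 | 28.6% | 34.8% |
| 1 | No | 6 | 14.3% | 18.2% |
| 0 | Yes | 7 | 0% | – |

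The per-cycle item flags one of the eight possible counts. The missed-day definition would flag seven of them. Non-last cycles with 1 to 4 injections sit in the lowest RDI class, below 62%, and still count as uninterrupted.

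**Three scheduled cycles.** Overall RDI = (75 × injections / total days)/18.75.

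| Injections per cycle | Missed of 21 | Per-cycle item: flag, cycles, days | Counted by day: flag, cycles, days | Overall RDI |
|---|---|---|---|---|
| 5/4/6 | 6 | No, 0, none | Yes, 3, 6 | 1125 mg/m² over 83 days = 72.3% |
| 7/0/7 | 7 | Yes, 1, 7 | Yes, 1, 7 | 1050 mg/m² over 84 days = 66.7% |
| 4/5/5 | 7 | No, 0, none | Yes, 3, 7 | 1050 mg/m² over 82 days = 68.3% |

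The last two patients miss the same number of injections and are classified oppositely.

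**The empty cycle.** For 7/0/7, if the entry rule is applied per drug, the patient has two azacitidine cycles, average days dosed per cycle is 14/2 = 7.0, and the flagged cycle is not among those entered. If the cycle is entered through S64315, the average is 14/3 = 4.67. The SAP does not say which applies.

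**Is there another trigger?** For cycle delay, SAP 4.2.1.5 supplements the e-CRF item with a rule based on administration dates. The interruption definition has no such supplement.

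**The case against.** The strongest objection is that the e-CRF cannot be seen and some SAP text suggests recording by day. Cycle delay is read from the same injection page, at D1 of the cycle. The number of days at the planned dose level needs a dose for each day. Counting cycles with at least one interruption is redundant if a cycle can hold only one answer. This evidence stands and keeps the per-cycle reading unproven. Against it, SAP 4.1.2 speaks of first and last intake dates by azacitidine cycle, which fits a cycle-level record.

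It can also be argued that a patient may need more than one injection on a dosing day: vials hold 100 mg, and at 75 mg/m² a body surface area above 100/75 = 1.33 m² needs more than one vial. The item would then make sense per day. This is weak, because the protocol counts one injection per day: section 10.2.6 counts injections out of 7, and Table (9.2.1) 1 labels the C1D2 and C1D3 doses as the second and third injections.

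Thirdly, the documents elsewhere use interruption for a 4-week hold, so flagging only empty cycles might be deliberate. That does not fit the SAP's own count of single missed days.

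Finally, the stakes are low, and this stands. RDI is reported in classes "overall, by cycle, and per treatment period (Combination treatment", which separate 7, 6, 5 and 4 or fewer injections in a full-dose 28-day non-last cycle. In the last cycle, 5 and 4 injections share one class. Days dosed and cumulative dose also show the misses. None of these corrects the flag, the cycle count or the days line.

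**Conclusion.** The concern holds, as a minor one. If the item is answered once per cycle, the definition is wrong as written: it misses every partly dosed cycle and drops patients who have only such cycles from the interruption-days line. In the example, 6 of 21 missed injections are reported as no interruption. If the item is answered per day, partial misses are caught, but the SAP still needs to say so and to state which answer counts.

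The per-cycle reading is an inference from the wording and from SAP 4.1.2; confidence in it is medium. The effect is confined to the four descriptive outputs named above. No DLT rule or dosing decision depends on the flag.

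**What to change.** In SAP 4.2.1.5, define an azacitidine interruption as at least one scheduled CxD1 to CxD7 injection not administered. Derive the Yes/No flag, the interrupted-cycle count and the interruption days from the day-level intake data already needed for the number of days dosed, so that all three use one definition. State how a scheduled cycle with no azacitidine injection is counted, given the cycle-entry rule. Report reasons only where the e-CRF collected them, and put the rest in the existing Missing class.

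If the item is in fact recorded per day, one sentence saying so and naming the answer that denotes an interruption is enough.

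The cost is a change of SAP wording and one derivation from data already required. Reasons for single missed days may not have been collected, so the Missing class could grow.
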